5.2.1.2 Performance of the BD NRFit™ Syringes

- Rate of successful aspiration of anesthetic through BD NRFit™ Syringes

A subject will be included in the analysis population if the following condition is met:

- Spinal Procedure Details – Syringe CRF page: 'Was a BD syringe NRFit used?' Equals 'Yes'

A successful aspiration of anesthetic through BD NRFit™ Syringe is defined as follows:

- 'Was anesthetic medication successfully aspirated through the BD NRFit syringe?' Equals 'Yes'

The incidence rate for this endpoint will be calculated as the number of participants experiencing the event divided by the total number of treated participants using the BD NRFit™ Syringes; 95% confidence interval (exact method) will be calculated.

- Rate of successful injection of anesthetic through BD NRFit™ Syringes

A subject will be included in the analysis population if the following condition is met:

- Spinal Procedure Details – Syringe CRF page: 'Was a BD syringe NRFit used?' Equals 'Yes'

A successful injection of anesthetic through BD NRFit™ Syringe is defined as follows:

- 'Was anesthetic medication successfully injected through the BD Syringe NRFit?' Equals 'Yes'

The incidence rate for this endpoint will be calculated as the number of participants experiencing the event divided by the total number of safety population using the BD NRFit™ Syringes; 95% confidence interval (exact method) will be calculated.

 BD	Statistical Analysis Plan	Page No.
	Study ID: MDS-21NRFit001	9 of 13

GFM-10082C

- Rate of BD NRFit™ Syringes that do not leak at the connection point during medication administration
A subject will be included in the analysis population if the following condition is met:
 - Spinal Procedure Details – Syringe CRF page: 'Was a BD syringe NRFit used?' Equals 'Yes'
A success of the endpoint for the BD NRFit™ Syringe is defined as follows:
 - 'Did the BD Syringe NRFit leak at the connection point during medication administration?' Equals 'No'

The incidence rate for this endpoint will be calculated as the number of participants experiencing the event divided by the total number of safety population using the BD NRFit™ Syringes; 95% confidence interval (exact method) will be calculated.

5.2.2 Primary Safety Endpoints

- Incidence of post dural puncture headache (PDPH)

The event of PDPH is defined as headache that worsens when standing/upright position and relieves when laying supine for a period of up to 10 (\pm 3 days) days following the procedure.

The incidence of PDPH will be based on response to the following question:

- "Post-dural Puncture Headache" CRF page: "Did the subject develop post-dural puncture headache (PDPH)?" Equals 'Yes'

Participants experiencing any severity (mild/moderate/severe) of PDPH will contribute to the incidence count in the numerator.

The incidence rate for the above primary safety endpoints will be calculated as the number of participants experiencing the event divided by the total number of safety participants defined in section 4.1; 95% confidence interval (exact method) will be calculated.

- Incidence of any BD NRFit™ spinal needle and BD NRFit™ introducer and BD NRFit™ syringe and procedure-related adverse events (other than PDPH)

Subject will be considered as having an event if the subject has the following responses for the questions on the AE CRF Page listed below:

THIS SUBJECT MATTER IS RESTRICTED SOLELY FOR THE USE OF BECTON DICKINSON AND COMPANY AND ITS SUBSIDIARIES

 BD	Statistical Analysis Plan	Page No.
	Study ID: MDS-21NRFit001	10 of 13

GFM-10082C

- Relationship to procedure: Equals 'Possible' or 'Probable' or 'Causal' OR
Relationship to spinal needle: Equals 'Possible' or 'Probable' or 'Causal'
OR Relationship to syringe: Equals 'Possible' or 'Probable' or 'Causal' OR
Relationship to introducer: Equals 'Possible' or 'Probable' or 'Causal'

The incidence rate for the above primary safety endpoints will be calculated as the number of participants experiencing the event divided by the total number of treated participants; 95% confidence interval (exact method) will be calculated.

THIS SUBJECT MATTER IS RESTRICTED SOLELY FOR THE USE OF BECTON DICKINSON AND COMPANY AND ITS SUBSIDIARIES

 BD	Statistical Analysis Plan	Page No.
	Study ID: MDS-21NRFit001	11 of 13

GFM-10082C

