## 8 PARTICIPANT DISCONTINUATION/WITHDRAWAL

### 8.1 Discontinuation/Withdrawal

- A participant may withdraw from the study at any time at his/her own request or may be withdrawn at any time at the discretion of the investigator or sponsor for safety, behavioral, compliance, or administrative reasons. This is expected to be uncommon.
- At the time of discontinuing from the study, no further data will be collected for the participant.
- If the participant withdraws consent from the study, he/she will inform the study physician who will record the withdrawal in the source documentation and appropriate section of the electronic case report form.
- If the participant withdraws consent for disclosure of future information, the sponsor may retain and continue to use any data collected before such a withdrawal of consent.
- Participants who withdraw or discontinue the study early (e.g., prior to day-10 post procedure follow-up or prior the procedure) may be replaced.

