### 8.2 Lost to Follow-Up

A participant will be considered lost to follow-up if he or she repeatedly is unable to be contacted by the study site.

Before a participant is deemed lost to follow up, the investigator or designee must make every effort to regain contact with the participant, where possible, with two telephone calls, or a message to the participant's last known mailing address or local equivalent methods. These contact attempts should be documented in the participant's medical record with possible reasons lost to follow-up, if available.

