## 10.4 General Considerations

Study endpoints may be missing due to reasons including lost to follow-up visits, procedures not being performed, or participant discontinuation. It is essential to minimize missing data and always record why it is missing. Analyses will be performed using evaluable data, combining all investigational sites. Statistical output will be generated using SAS (SAS Institute, Cary, NC) version 9.4 or above.

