### 10.5.2 Primary Safety Endpoints

- Incidence of post dural puncture headache (PDPH)

The event of PDPH is defined as headache that worsens when standing/upright position and relieves when laying supine for a period of up to 10 ( $\pm$  3 days) days following the procedure.

The incidence rate for the above primary safety endpoints will be calculated as the number of participants experiencing the event divided by the total number of safety participants; 95% confidence interval (exact method) will be calculated.

- Incidence of any BD NRFit™ spinal needle and BD NRFit™ introducer and BD NRFit™ syringe and procedure-related adverse events (other than PDPH)

The incidence rate for the above primary safety endpoints will be calculated as the number of participants experiencing the event divided by the total number of treated participants; 95% confidence interval (exact method) will be calculated.

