4.0 ANALYSIS POPULATION SET(S)

4.1 Populations Definitions

The following populations are defined in the table below:

Table 4. Population Definitions

Population	Description
Enrolled	All participants who sign the ICF
Treated	All participants in whom a spinal anesthesia procedure is attempted, regardless of success
Safety	All participants in whom a spinal anesthesia procedure is successful

Treated population will include the following participants on the Spinal Procedure CRF page:

- 'Was spinal procedure performed or attempted using BD NRFit devices?' Equals 'Yes'.

Safety population will include the following participants on the Spinal Procedure Details - BD NRFit Needle CRF page:

- 'Was there a spontaneous appearance of cerebrospinal fluid (CSF) emerging from the needle hub?' Equals 'Yes'.

The primary performance endpoints analysis will be performed on the treated population. The primary safety endpoint analysis for PDPH incidence will be performed on the safety population. The primary safety endpoint analysis for device/procedure-related adverse events (other than PDPH) will be performed on the treated population.

THIS SUBJECT MATTER IS RESTRICTED SOLELY FOR THE USE OF BECTON DICKINSON AND COMPANY AND ITS SUBSIDIARIES

 BD	Statistical Analysis Plan	Page No.
	Study ID: MDS-21NRFit001	7 of 13

GFM-10082C

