5.2 Analysis Methods

5.2.1 Primary Performance Endpoints

5.2.1.1 Performance of the BD Spinal NRFit™ Needle and BD NRFit™ Introducer

- Rate of successful BD Spinal NRFit™ Needle placement

The successful placement of the BD Spinal NRFit™ needle in the subarachnoid location is defined as the spontaneous appearance of cerebrospinal fluid (CSF) emerging from the spinal needle hub. In case of multiple attempts, successful placement is determined by the last attempt.

It will be computed as the number of participants experiencing the event divided by the total number of subjects with needles attempted; 95% confidence interval (exact method) will be calculated. The analysis will be performed on the treated population as defined in section 4.1.

The incidence of successful needle placement will be based on counts of "Yes" response to the following question on the "Spinal Procedure Details - BD NRFit Needle" CRF page: "Was there a spontaneous appearance of cerebrospinal fluid (CSF) emerging from the needle hub?"

- Rate of successful BD Spinal NRFit™ Needle placement when a BD Spinal NRFit™ Introducer is used

The successful placement of the BD Spinal NRFit™ needle in the subarachnoid location is defined as the spontaneous appearance of cerebrospinal fluid (CSF) emerging from the spinal needle hub for subjects who used BD NRFit™ introducer. In case of multiple attempts, successful placement is determined by the last attempt. If a subject uses BD NRFit™ introducer for the last attempt, the subject will be considered as part of the introducer population.

The incidence rate for the primary performance endpoints will be calculated as the number of participants experiencing the event divided by the total number of treated participants using BD NRFit™ introducer; 95% confidence interval (exact method) will be calculated.

A subject will be included in the analysis population if both of the following two conditions are met:

- Spinal Procedure CRF page: 'Was spinal procedure performed or attempted using BD NRFit devices?' Equals 'Yes'

THIS SUBJECT MATTER IS RESTRICTED SOLELY FOR THE USE OF BECTON DICKINSON AND COMPANY AND ITS SUBSIDIARIES

 BD	Statistical Analysis Plan	Page No.
	Study ID: MDS-21NRFit001	8 of 13

GFM-10082C

- AND

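### SAP 5.2.2 counts a participant never assessed for PDPH as PDPH-free if read literally, and its event rule for the second primary safety endpoint does not remove PDPH

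*SAP*

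**What the plan says.** **PDPH rate.** Under SAP 5.2.2 a participant is an event if the PDPH page of the CRF is answered 'Yes'. The number of events is "divided by the total number of safety participants defined in section 4.1". Protocol 10.5.2 has the same denominator: "divided by the total number of safety participants; 95% confidence interval (exact method) will be calculated". SAP 4.1 puts a participant in the safety population on one procedure-day answer: "Was there a spontaneous appearance of cerebrospinal fluid (CSF) emerging from the needle hub". Follow-up plays no part.

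**Missing data.** Protocol 10.4 expects endpoints to be missing through loss to follow-up or discontinuation and then says: "Analyses will be performed using evaluable data, combining all investigational sites". It does not say what evaluable means for PDPH, and the SAP has no missing-data rule. Protocol 8.1 adds: "At the time of discontinuing from the study, no further data will be collected for the participant". Protocol 8.2 defines loss: "A participant will be considered lost to follow-up if he or she repeatedly is unable to be contacted by the study site". On replacement, Protocol 8.1 says: "Participants who withdraw or discontinue the study early (e.g., prior to day-10 post procedure follow-up or prior the procedure) may be replaced".

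**Second primary safety endpoint.** Protocol 10.3 and 10.5.2 and SAP 4.1 and 5.2.2 all name it as related adverse events other than PDPH. The event rule in SAP 5.2.2 joins four relatedness fields (procedure, needle, syringe, introducer) by OR, each met by 'Possible', 'Probable' or 'Causal'. It has no step that removes PDPH. In SAP 1.2 the objective carries the exclusion, but the endpoint beside it does not.

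**Criterion.** SAP 1.3 asks that observed PDPH incidence be at most 3%, in line with literature data.

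**The concern.** A participant with a successful procedure who is then lost adds nothing to the numerator and one to the denominator. If that participant had an unrecorded PDPH, the printed rate is too low and its interval too narrow, and for a safety endpoint that error favours the device. If none of the lost had PDPH, the literal rate is right. The evaluable-data sentence in Protocol 10.4 points to a different denominator, so two programmers could print different rates from the same data.

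The second endpoint has a different gap: the rule to be programmed does not do what its name says. The Protocol synopsis treats PDPH as an adverse event. A PDPH that also appears on the AE page with at least a possible relationship would be counted in an endpoint meant to exclude it.

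**Working it through.** **Inputs.** About 150 treated (SAP 2.4); criterion at most 3% (SAP 1.3); exact 95% interval (SAP 5.2.2). The documents give no loss rate, so 5%, 10% and 15% are assumptions: 8, 15 or 22 of 150 unassessed, leaving 142, 135 or 128.

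**The plan's own figures.** The exact (Clopper-Pearson) half-width at n = 150 and rate 3% (4.5 events by beta quantiles) is 3.12%, which matches the stated 3.1%. The chance of at least one event at a 1% rate is 1 − 0.99^150 = 0.7785, which matches 77.9%.

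**Average printed rate.** If loss is unrelated to PDPH and events among the lost go unrecorded, the literal rate averages (true rate) × (assessed / 150). At a true 4%:
- 142 assessed: 4% × 142/150 = 3.79%
- 135 assessed: 4% × 135/150 = 3.60%
- 128 assessed: 4% × 128/150 = 3.41%

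**When the 3% result changes at 150.** Four events meet the criterion only if the denominator is at least 4/0.03 = 133.3, that is 134. So 150 − 133 = 17 unassessed (11.3%) are needed.

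| Denominator | Rate with 4 events | Exact 95% CI |
|---|---|---|
| 150 (literal) | 2.67% | 0.73–6.69% |
| 142 (8 unassessed) | 2.82% | 0.77–7.06% |
| 135 (15 unassessed) | 2.96% | 0.81–7.41% |
| 133 (17 unassessed) | 3.01% | 0.83–7.52% |

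Five events fail even at 150 (3.33%). Three events would need 51 unassessed. Exactly 4 recorded events among 133 has probability 0.198 at a true 3% and 0.165 at 4%.

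**Chance of printing at most 3% at a true 4%**, with events among the lost unrecorded: 0.280 if all 150 are assessed; 0.369 under both denominators with 135 assessed, because the cut-off is still 4 events; 0.416 literal against 0.243 known-status with 128 assessed.

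**Other set sizes.** About 180 are enrolled to treat at least 150. At 167–180 the result changes with 5 events and 1–14 unassessed, for example 5/170 = 2.94% against 5/162 = 3.09%. At 135 (placement success at the 90% floor) it takes 4 events and 2 unassessed.

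**Bounds.** With 4 events in 150 and 8 unknown: 4/150 = 2.67% (unknown = no event), 4/142 = 2.82% (known only), 12/150 = 8.00% (unknown = event).

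**Second endpoint.** The documents do not show whether PDPH is also entered on the AE page. As an illustration with assumed counts, 6 participants with other related events and 4 more with related PDPH give 6/150 = 4.0% under the name and 10/150 = 6.7% under the rule.

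**The case against.** The strongest reply is that Protocol 10.4 already covers this: it names loss and discontinuation as causes of missing endpoints and then requires evaluable data. Protocol section 10 presents the SAP as adding detail to those analyses. On that reading an unassessed participant is already outside the rate, and only a definition is missing. Much of this stands. It means the understated rate is one reading of the plan and not its settled rule. It does not remove the conflict, because both SAP 5.2.2 and Protocol 10.5.2 still divide by the total number of safety participants.

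The effect is also likely to be small. Follow-up lasts 10 days, telephone contact is allowed, and Protocol 8.1 expects withdrawal to be uncommon. Protocol 7.4.1 places PDPH within 5 days and Protocol 3.1 within 7, so late loss should cost little. SAP 6.1 and 6.7 will show the losses, although they do not change the printed rate.

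A reader might infer three stronger claims that the documents do not support:
- That the SAP treated PDPH differently from other primary endpoints, since needle placement is "divided by the total number of subjects with needles attempted". That narrowing, like those for introducer and syringe, concerns device use. None of it removes a missing answer.
- That replacement is a separate defect. Keeping a treated, replaced participant in the safety set is proper. With 17 lost and replaced, 5/167 = 2.99% against 5/150 = 3.33% is the same denominator question.
- That it is undecided whether the second endpoint excludes PDPH. Four sections say it does; only the event rule fails to apply it.

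Limiting the PDPH rate to successful procedures is a consistent prespecified choice and is not at issue.

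**Conclusion.** Both points hold and should be corrected before database lock; neither overturns the study.

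Read literally, SAP 5.2.2 classes unassessed participants as PDPH-free, against the evaluable-data principle in Protocol 10.4. Relative to the true incidence in the safety set, the literal rate can only be right or too low. At assumed losses of 5–15% unrelated to PDPH, with events among the lost unrecorded, a true 4% prints on average as 3.79% to 3.41%.

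It would be too strong to say that the 3% result is in general danger. At 150 the two denominators disagree only with exactly 4 events and at least 17 unassessed. Sets of 167–180 are more sensitive, but need nearly all of the roughly 180 enrolled to have a successful procedure. The criterion is descriptive, and the shift at the tipping point (2.67% to 3.01%) is small against an interval of roughly 0.7% to 7%.

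For the second endpoint, the rule as written contradicts its own name. The size of any double count is unknown, and this endpoint has no acceptance criterion.

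**What to change.** 1. In SAP 5.2.2, make the PDPH denominator the safety participants with known PDPH status, citing Protocol 10.4.
2. Define known status before database lock. One workable rule is 'Yes' at any time, or a documented 'No' from the follow-up assessment in its 10 (±3) day window. State how an earlier 'No' followed by loss is classified. If 5 of 8 lost participants had one, 4 events give 4/142 = 2.82% or 4/147 = 2.72%, depending on that choice.
3. Report the number unknown, and show the rate with all unknowns as no event and as event. These bounds are necessary because the rule in step 2 keeps early events but drops early non-events. With 15 of 150 lost, one of the 4 events recorded among them and no PDPH in the other 14, it gives 4/136 = 2.94% against 4/150 = 2.67%.
4. Say that replaced participants follow the same rule.
5. Add to the related-AE event rule the condition that the event is not PDPH, and align the endpoint wording in SAP 1.2.

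The cost is SAP wording and a few table rows, with no new data. The PDPH rate may be slightly less favourable and its interval slightly wider, and the upper bound will look high if many are lost. The Protocol need not change. Rewording Protocol 10.5.2 as well would need an amendment with IRB/EC notification and, as applicable, approval (Protocol 14.1).

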6.0 SUMMARY OF GENERAL STUDY DATA

6.1 Subject/Sample Disposition

The summary of the number of subjects in the enrolled population, treated population, safety population, as well as those that completed the study, and withdrew from the study with reason for withdrawal will be provided. Screen Failures will be summarized for each inclusion/exclusion criteria that was not met. Summary table will also be provided by site.

6.2 Protocol Deviations

A protocol deviation is defined as an event where the Investigator or site personnel did not conduct the study according to the protocol requirements. Any and all protocol deviations must be documented regardless of whether medically justifiable, Sponsor-approved or taken to protect the subject in an emergency. Details regarding protocol deviations will be listed for enrolled participants.

6.3 Demographics and Baseline Variables

Demographics and baseline characteristics will be summarized with descriptive statistics for treated population. Summary statistics for categorical variables will include frequency and percentages, and for continuous variables will include mean, standard deviation (SD), minimum, median, and maximum. Demographic data (age (at signing informed consent), gender, race, body height, body weight, body mass index (BMI)) will be tabulated.

The demographic variables will include:

- Age (at signing informed consent)
- Sex
- Race
- BMI
- Body Weight
- Body Height

6.4 Concurrent Illnesses and Medical Conditions

Medical history will be summarized with descriptive statistics for the treated population.

6.5 Prior and Concurrent Medications

Not Applicable.

6.6 Study Device Procedure

The data related to study device details and placement are recorded on the Procedure section of eCRF page. The device procedure data will be summarized separately for spinal procedure, syringe, BD NRFit™ Needle type, BD NRFit™ Introducer type and ease of use procedure survey for the treated population. The reason for surgery and

THIS SUBJECT MATTER IS RESTRICTED SOLELY FOR THE USE OF BECTON DICKINSON AND COMPANY AND ITS SUBSIDIARIES

 BD	Statistical Analysis Plan	Page No.
	Study ID: MDS-21NRFit001	12 of 13

GFM-10082C

for neuraxial procedure as well as the ASA classification will be also listed and tabulated.

6.7 Follow-up Visit Summary

Follow-up visit summary and listing will be presented for the treated population.

6.8 Device Failure, Malfunctions and Defects

Device failures, malfunctions or defects will be tabulated and presented on participant level for treated population. Details regarding device deficiencies will be listed.

7.0 SAFETY ANALYSIS

An overall summary including the number and percentage of subjects with at least one AE, total number of AEs, total number of SAEs, AEs by relationship to the Device/Index Procedure, and AEs by severity of the event will be summarized for the treated population.

AEs will be coded by using the medical dictionary for regulatory activities version 26.0 (MedDRA). All verbatim terms will be coded to the lowest level term (LLT) and will be classified by primary System Organ Class (SOC) according to the MedDRA thesaurus. AEs will be tabulated by SOC and Preferred Term (PT). The number of entries, as well as the number and rate of affected participants will be reported. Additionally, AEs will be presented by severity.

SAEs and AEs which are related to device (adverse device effects [ADEs]), AEs which are related to procedure, or related to accessories (stylet and introducer) will be presented separately. All AEs will be listed together with start date of AE as well as duration of AE for AEs with complete dates.

THIS SUBJECT MATTER IS RESTRICTED SOLELY FOR THE USE OF BECTON DICKINSON AND COMPANY AND ITS SUBSIDIARIES

 BD	Statistical Analysis Plan	Page No.
	Study ID: MDS-21NRFit001	13 of 13

GFM-10082C

